**\*Please enter the Protocol Number you would like to use to reference the protocol:**

380797

\* This field allows you to enter an abbreviated version of the Protocol Title to quickly identify this protocol.

**Is this a multi-site study (i.e. Each site has their own Principal Investigator)?**

No

**Does this protocol involve the use of animals?**

Yes  No

**4.0 Project Information**

**4.1 Is this a research study?**

Yes  No

**4.2 What type of research is this?**

- Biomedical Research
- Clinical trial (FDA regulated)
- Behavioral Research
- Educational Research
- Psychosocial Research
- Oral History

Other

**4.4 Is this human subjects research (Activities that include both a systematic investigation designed to develop or contribute to generalizable knowledge AND involve a living individual about whom an investigator conducting research obtains data through intervention or interaction with the individual or identifiable private information. Activities covered by 32 CFR 219.101(a) (including exempt research involving human subjects) and DoDI 3216.02)?**

Yes  No

**4.5 Do you believe this human subjects research is exempt from IRB review?**

Yes  No

## 5.0 Personnel Details

**5.1 Will you have a Research Monitor for this study?**

Yes  
 No  
 N/A

Research Monitor Role:

Research Monitor will be responsible to promptly report any observations and findings to the Institutional Review Board (IRB), the Human Protections Administrator (HPA), or the Institutional Official. The research monitor will review the study monitoring plans, review Adverse Events and determine their relatedness to the protocol, review Unanticipated Problems Involving Risks to Subjects of Others, make recommendations on changes to the informed consent process based on the review of study events, and review and sign the continuing review report. The monitor will notify the IRB or HPA if you will not be able to fulfill your duties due to reassignment, retirement, deployment, or change of responsibilities. A replacement Research Monitor will need to be assigned and approved.

If applicable, you may nominate an individual to serve as the Research Monitor:

	Selected Users
	[name]
	[name]

## 6.0 Data/Specimens

**6.1 Does the study involve the use of existing data or specimens only (no interaction with human subjects)?**

Yes  No

## 7.0 Funding and Disclosures

### 7.1 Source of Funding:

Funding Source	Funding Type	Amount
Congressionally Directed : Medical Research Program (CDMRP)  DOD - MRMC	Research Development : Testing and Evaluation (RDT&E) funds	1948488

Total amount of funding:

1948488

### 7.2 Do you or any other Investigator(s) have a disclosure of a personal interest or financial nature significant with sponsor(s), product(s), instrument(s) and/or company(ies) involved in this study?

Yes  No

### 8.2 Has another IRB reviewed this study?

Yes  No

IRB Name	Review Date	Determination
USUHS IRB : #1  If other, please define:  	04/22/2016	Approved via expedited procedures  Other Determination:  Secondary Concurrence of CR

### 8.3 Is this a collaborative or multi-site study? (e.g., are there any other institutions involved?)

Yes  No

### 8.5 Are there international sites?

Attach international approval documents, if applicable, when prompted. Note: Ensure local research context has been considered

Yes  No

### 8.6 Is this an OCONUS (Outside Continental United States) study?

Yes  No

Select the area of responsibility:

Have you obtained permission from that area of responsibility? (This is a requirement prior to study approval)

Yes  No

## 9.0 Study Details

### 9.1 Abstract/ Summary:

Summarize the proposed study in 500 words or less, to include the purpose, the subject population, the study's design type, and procedures

Riluzole is a glutamatergic modulator that inhibits glutamate release and enhances AMPA trafficking and clearance of excessive synaptic glutamate resulting in neuroprotective properties. Riluzole is FDA-approved for the treatment of amyotrophic lateral sclerosis (ALS) and has been found to have antidepressant and anxiolytic properties in animals and in humans (Zarate et al., 2004). Posttraumatic stress disorder (PTSD) is a chronic and seriously debilitating anxiety disorder that develops following exposure to severe trauma, such as combat exposure. Structural magnetic resonance imaging has been used to measure the volume of crucial structures implicated in the pathophysiology of PTSD, with several morphometric studies confirming smaller hippocampal volume in PTSD patients. Current

pharmacological treatment for PTSD, and particularly combat-related PTSD, is suboptimal. Drugs that alter neuronal survival pathways through reduction of glutamate activity may play a role in reversing the loss of neuronal integrity and possible focal atrophy in regions of the brain implicated in the pathophysiology of PTSD, potentially improving the symptoms of PTSD, as well as TBI.

This study will evaluate the efficacy of acute riluzole treatment in active duty and Operation Iraqi Freedom (OIF), Operation Enduring Freedom (OEF), and Operation New Dawn (OND) veterans with PTSD, with or without mild TBI (mTBI), who are sub-optimally responsive to other medication treatments. A total of 158 active duty and OIF, OEF and OND veterans, aged 18 to 65 will be enrolled from WRNMMC and the Syracuse VA Medical Center to participate in this 8-week randomized, double-blind, placebo-controlled, parallel study. Patients who are suboptimal responders to their current psychotropic drugs will continue these at stable dosage for at least 2 weeks prior to randomization during the screening period. We hypothesize that those subjects with PTSD, with or without mTBI, who are only partially responsive to initial therapy and are subsequently randomized to augmentation therapy with Riluzole (100-200mg/day) will have a superior response rate compared to those subjects randomized to placebo.

## 9.2 Key Words:

Provide up to 5 key words that identify the broad topic(s) of your study

---

## 9.3 Background and Significance:

Include a literature review that describes in detail the rationale for conducting the study. Include descriptions of any preliminary studies and findings that led to the development of the protocol. The background section should clearly support the choice of study variables and explain the basis for the research questions and/or study hypotheses. This section establishes the relevance of the study and explains the applicability of its findings

### **An over-simplification of the Research Proposal:**

A service member experiences a physical and or emotional stressor during combat. The release of glutamate (from stress or brain injury) along with higher levels of glucocorticoids (endogenous cortisol) is toxic to the hippocampus causing a constellation of symptoms defined as PTSD. The neurotoxic effects on the hippocampus are part of the picture; the effects of glutamate on the ability to extinguish fear memory is really what we are concerned about as failure to extinguish fear memory (that is failure to learn to forget) seems to be the process responsible for the intrusive recollections and excessive over-generalized response to new stimuli we observe in PTSD. The challenge is that increased concentrations of glutamate in the brain have been linked to a variety of cognitive effects included over-excitation, neurodegeneration and impaired neuronal plasticity, and many of the associated symptoms such as impaired memory, depression and chronic stress are also correlated with PTSD. Whether PTSD is solely a direct result of changes in glutamate concentration is an open question.

### **Posttraumatic stress disorder (PTSD)**

PTSD is a chronic anxiety disorder that develops in approximately one fifth of individuals exposed to severe trauma (Kessler et al., 1995; Breslau et al., 1998). Rates of PTSD in returning OIF and OEF active duty soldiers are between 6 and 19% (Hoge et al., 2004; Hoge et al., 2007; Friedman, 2007; Erbes et al., 2007). Over 20% of those injured in Iraq have suffered head/brain injuries that require lifetime continual care and rates of TBI have been estimated as high as 30%. The presence of PTSD in patients with TBI can be difficult to identify and treat. Although TBI and PTSD are among the most common disorders as a result of the OIF and OEF missions, currently available treatments are not targeted towards this group. A recent Institute of Medicine (IOM) review found insufficient evidence to support the efficacy of any single pharmacologic agent for PTSD (IOM, 2007). While the American Psychiatric Association's 2009 Practice Guideline Watch and the most recent DoD-VA practice guideline suggest that there is growing evidence for the efficacy of certain pharmacologic treatments, studies suggest these treatments may not be effective for combat-related PTSD (DoD-VA Practice Guideline for the Management of Posttraumatic Stress, 2010)).

### **Medication Treatments for PTSD**

Selective serotonin re-uptake inhibitors (SSRIs) are currently the only class of FDA-approved medications available for the treatment of PTSD. Although studies demonstrating the efficacy of SSRIs in PTSD use well-designed, double-blind strategies, the results are inconsistent, producing low to

moderate effect sizes (0.3 to 0.5) (Van der Kolk et al., 1994; Conner et al., 1999; Martenyi et al., 2002; Brady et al., 2000; Davidson et al., 2002; Marshall et al., 2001; Tucker et al., 2007), or no significant effect at all (Friedman et al., 2007; Zohar et al., 2002; Martenyi et al., 2007; Van der Kolk et al., 2007), compared to placebo (Pitman et al., 2002). Prazosin, a centrally active alpha-1 adrenoceptor antagonist, reduced nightmares associated with PTSD in addition to overall PTSD symptoms when used as an adjunct to other psychotropic medications in PTSD (Raskind et al., 2007; Peskind et al., 2003). Other novel pharmacological strategies, including low dose cortisol (Aerni et al., 2004) have provided limited reduction in PTSD symptoms, but need further investigation.

In summary, for patients with PTSD, existing medication treatment options are suboptimal. Therefore, there is an urgent need for the development of novel interventions for PTSD that rapidly and robustly improves PTSD symptoms with minimal side effects.

### **The Role of Glutamate in acute and chronic stress: Pre-clinical models**

Glutamate is an excitatory amino acid that has been implicated in the pathophysiology of major depression, TBI, Huntington's disease, and Alzheimer's disease (Hynd et al., 2004; Benn et al., 2007). Glutamate plays a crucial role in acute and chronic neurodegeneration, as well as neural plasticity (Einat & Manji, 2006; Parsons et al., 2007; Du et al., 2004). The stress-related effects of glucocorticoids and the excitatory effect of glutamate on the hippocampus make this brain region susceptible to damage following the experience of a stressor. For example, corticosterone has been found to prolong NMDA receptor-mediated calcium activation (Sato et al., 2004) and reduce plasticity of the hippocampus, also via NMDA receptors (McEwen et al., 2000). It appears that stress increases levels of glutamate which may be neurotoxic, particularly to the hippocampus; whereas drugs that reduce glutamatergic neurotransmission are neuroprotective and improve symptoms in preclinical models of chronic stress and depression. While there have not been studies of the direct effects of cortisol administration on PTSD, drugs that more tightly regulate glutamate brain concentrations by either decreasing glutamate release or activity or enhance its uptake could provide a novel strategy to reduce symptoms of PTSD and alleviate distress in this chronic stress disorder.

### **Is PTSD associated with impairment of neural plasticity and cellular resilience?**

Yes, a very rough outline of this connection is based on increased glutamate levels triggering prolonged LTP causing stressful or highly emotional memories to become associated with non-stressful events. This results in someone displaying heightened stress responses to otherwise mundane situations, a hallmark symptom of PTSD.

Structural magnetic resonance imaging has been used to measure the volume of crucial structures implicated in the pathophysiology of PTSD. Several (Carrion et al., 2007; Pavic et al., 2007; Bremner et al., 2005; Vythilingam et al., 2005), but not all (Jatzko et al., 2006; Woodward et al., 2006; Pederson et al., 2004), morphometric studies have confirmed smaller hippocampal volume in PTSD patients, compared to controls. A recent meta-analysis of valid structural MRI studies in PTSD also confirmed a smaller hippocampal volume in this disorder (Karl et al., 2006). Volumetric reduction in the anterior cingulate appears to be a consistent finding in PTSD, as well (Kasai et al., 2007; Kim et al., 2007; Rauch et al., 2003). The only postmortem study in PTSD confirmed neuronal loss in the locus coeruleus (LC) in combat veterans, compared to controls (Bracha et al., 2005).

Proton magnetic resonance spectroscopy ( $^1\text{H}$  MRS), an in vivo imaging technique, provides direct neurochemical information in the brain. NAA levels that were measured using  $^1\text{H}$  MRS served as a surrogate marker for neuronal integrity and reflected the extent of neuronal loss or injury (Sager et al., 2001; Ebisu et al., 1994). Reduced levels of NAA/Cr ratio in the hippocampus and anterior cingulate have been reported in patients with PTSD due to mixed traumas (Mahmutyazicioglu, 2005), in fire survivors (Li, 2006) and in combat veterans (trend) (Villareal et al., 2002). Reduced NAA/Cr ratio was also reported in the anterior cingulate of maltreated children (De Bellis, 2000) and in the basal ganglia of adolescent fire survivors with PTSD (Lim et al., 2003). Studies that attempted to differentiate traumatized subjects with and without PTSD using NAA/Cr ratio reported no differences; however, small sample sizes may have been a limitation (Seedat et al., 2005; Kimbrell et al., 2005).

Patients with ALS demonstrated a significant increase in NAA/Cr ratio in the motor cortex following 3-week treatment with 100mg of riluzole daily (Kalra et al., 1998). Riluzole may result in rapid improvement of neuronal integrity, as an increase in the NAA/Cr ratio was found as early as 1 day following treatment with riluzole in ALS patients (Kalra et al., 2006). Patients with Generalized anxiety disorder (GAD) who responded to 8 weeks of riluzole treatment (9 of 14, 64%) demonstrated a significant increase in hippocampal NAA using  $^1\text{H}$  MRS in contrast to a decrease in NAA levels in non-responders (Mathew et al., 2008). The effects of riluzole treatment on hippocampal and anterior cingulate NAA levels in PTSD have not yet been assessed.

Structural MRI studies of the pathophysiology of PTSD have not established a correlation between LC neuronal loss and volumetric loss for the hippocampus and the ACC, possibly due to methodologies with

study sampling and design. While several of these studies investigated mixed traumas, these were in exclusively in civilian settings. Few studies have considered the subset of combat-trauma exposure, which we believe is an entirely unique presentation. The 2005 Bracha et al. finding of postmortem LC neuronal loss in combat veterans could indicate such a correlation, hence the decision to pursue structural MRI analysis in this trial.

Taken together, current data suggest the loss of neuronal integrity and possible focal atrophy in regions of the brain are implicated in the pathophysiology of PTSD. Drugs that alter neuronal survival pathways through reduction of glutamate activity may play a role in reversing these effects and improving symptoms of PTSD, as well as TBI. Given that the neuropsychiatric community continues to refine clinically significant diagnostic points of departure for co-morbidity, it remains challenging to distinguish clearly PTSD and TBI with regard to symptomology and clinical outcomes. Nowhere is this more clearly evident than in the overlapping associated symptoms of PTSD and Persistent Post-concussive Syndrome (TBI), which include depression, anxiety, insomnia, irritability/anger, poor concentration, fatigue, hyperarousal, and avoidance. As research into this field continues, characterization of the neurological change from each diagnosis may become more likely.

TBI is frequently diagnosed in comorbidity with PTSD and, as a result, it is nearly impossible to find a sufficient sample of PTSD patients in combat veteran populations. Because the goal of this study is to provide an empirical assessment of whether riluzole is an effective treatment in real world, combat veteran PTSD populations, the effect of riluzole on TBI symptoms is not one of our objectives. This is why we are concerned only in the efficacy of treating PTSD in patients regardless of their TBI history. However, there is ample evidence within the field that brain injury is associated with increased glutamate concentrations in the brain. Chamoun et al (2010) provides strong evidence that increased levels of glutamate following a traumatic brain injury are strongly predictive of poorer outcomes.

### **Riluzole (Rilutek®)**

Riluzole, a neuroprotective agent with anticonvulsant properties, is a member of the benzothiazole class. Chemically, riluzole is 2-amino-6-(trifluoromethoxy) benzothiazole. Riluzole is the only drug currently approved (by the FDA in US, CPMP in Europe and MHW in Japan) for the treatment of ALS. Riluzole is an antagonist at a subset of Glu receptors (Benavides 1985), functional antagonist at NMDA and kainate receptors (Debono, 1993), and noncompetitive antagonist of AMPA receptors in the rat spinal cord (Albo, 2004) and cortex (Zona, 2002). Riluzole also inhibits the release of Glu in vivo (Cheramy, 1992) and in vitro (Doble, 1992; Martin, 1993; Jehle, 2000). Riluzole interacts with a large number of ion channels (voltage-activated sodium channels) (Benoit, 1993; Hebert, 1994; Zona, 1998; Urbani, 2000), voltage-gated calcium channels (VGCCs) (Huang et al., 1997; Stefani et al., 1997), and voltage-gated potassium channels (Zona, 1998; Duprat, 2000; Xu, 2001; Ahn, 2005; Ahn, 2006) that may contribute to a reduction in Glu release (Cheramy et al., 1992) and its neuroprotective effects. It enhances AMPA trafficking and increases glial uptake of glutamate (Azbill, 2000; Dunlop, 2003). Upregulation of glial Glu reuptake results in decreased extrasynaptic Glu concentrations and a release from the tonic inhibition of these neurons by activation of the presynaptic mGluR 2/3 receptors. This finding could offer an explanation for how riluzole induces trophic factors, including BDNF (Mizuta, 2001; Katoh-Semba, 2002). The interaction of BDNF with other trophic factors is a matter of scientific debate in the published literature and is beyond the scope of a clinical trial. Elucidation of BDNF biochemistry would be more appropriate in a cell culture or rodent model investigation. As such, a more descriptive presentation would neither strengthen the protocol nor provide necessary information for the participant in their process of granting informed consent. Further, any attempt would be beyond the reading comprehension level implicit and necessary in the Consent Form. While we consider it a fair point for the Reviewer to raise, we respectfully submit that it is beyond the scope of this trial.

In summary, preclinical and clinical data suggest that dysfunction in glutamatergic neurotransmission is a prime candidate in the pathophysiology of PTSD. The antiglutamatergic agent riluzole appears to have significant neuroprotective effects and the potential to be a novel agent in the treatment of PTSD. This study will permit us to determine the therapeutic benefit of reducing glutamate activity in subjects with PTSD.

### **Scientific Justification.**

Scientific justification for the proposed research, as well as rationale for the research hypotheses, is detailed in the preceding Section.

### **Human Subjects Justification.**

For patients with PTSD, existing medication treatment options are suboptimal. Current research suggests that the loss of neuronal integrity and possible focal atrophy in regions of the brain are implicated in the pathophysiology of PTSD, and drugs that alter neuronal survival pathways through the reduction of glutamate activity may play a role in reversing these effects and improving symptoms of PTSD, as well as TBI. Riluzole is an FDA-approved drug for the treatment of ALS, and research indicates

that it may result in rapid improvement of neuronal integrity, as an increase in the NAA/Cr ratio was found as early as 1 day following treatment with riluzole in ALS patients (Kalra et al., 2006). However, the effects of riluzole treatment on hippocampal and anterior cingulate NAA levels in PTSD have not yet been assessed, despite the drug appearing to have significant neuroprotective effects and the potential to be a novel agent in the treatment of PTSD. This study will permit us to determine the therapeutic benefit of reducing glutamate activity in subjects with PTSD with minimal side effects.

#### 9.4 Objectives/Specific Aims/Research Questions:

Describe the purpose and objective(s) of the study, specific aims, and/or research questions/hypotheses

**Objective:** To evaluate the efficacy of acute riluzole treatment (100-200mg/day) in 158 active duty and returning OIF, OEF, and OND veterans, aged 18 to 65 with a diagnosis of PTSD, with or without mTBI, who are sub-optimally responsive to their current medication treatment (8 weeks).

**Hypothesis 1:** *Subjects with PTSD, with or without mTBI, who are only partially responsive to initial therapy (e.g., CAPS score greater than or = 40 at the completion of an adequate trial of medication therapy) who are subsequently randomized to augmentation therapy with riluzole will have a superior response rate compared to subjects randomized to placebo.*

**Hypothesis 2:** *PTSD patients randomized to augmentation with riluzole therapy will have significant improvement in depression, anxiety and global functioning compared to those who receive placebo in addition to their pre-study PTSD medication.*

**Hypothesis 3:** *The N-acetyl aspartate to creatine ratio (NAA/Cr) in the hippocampus and anterior cingulate, measured using magnetic resonance spectroscopy (H MRS), will increase after 8-week treatment with riluzole.*

In addition to indicating simple change in severity, the change in CAPS total score will be the primary outcome variable at the end of Phase II (Visit 10). We believe this study is powered to detect a 9 point or greater difference in CAPS total score from baseline between riluzole and placebo augmentation (after Phase I) to the last measured value of Phase II.

The following scales are proposed for primary and secondary outcome measures:

- i. Primary Outcomes Assessment:** Clinician-Administered PTSD Scale (CAPS), Clinical Global Impression of Severity (CGI-Severity), Clinical Global Impression of Improvement (CGI-Improvement).
- ii. Secondary Outcomes Assessment:** Montgomery-Asberg Depression Rating Scale (MADRS), Hamilton Anxiety Rating Scale (HAM-A), Sheehan Disability Scale (SDS), PTSD Checklist (PLC-C), UKU Side Effect Rating Scale, Self-rating version.
- iii. Additional secondary outcome measure:** Changes in NAA levels in the hippocampus and anterior cingulate cortex following riluzole or placebo administration measured using H MRS.

Further, these scales are proposed as **Additional Measurement Instruments:** Liebowitz Social Anxiety Scale (LSAS), Pittsburgh Sleep Quality Index (PSQI), Dissociative Experience Scale (DES), World Health Organization Quality of Life (WHOQOL-BREF), Connor-Davidson Resilience Scale (CD-RISC), Childhood Trauma Questionnaire, Short Form (CTQ-SF), Symptom Checklist, 90 items, Revised (SCL-90-R), Peri Traumatic Distress Inventory (PDI).

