### a. Method of Collection from Study Participants.

**Primary Outcomes Assessment** – All study assessment materials are in the public domain and will not be altered. Each measure includes a minimum of one citation attesting to the reliability and validity of

the questionnaire based on the consensus of researchers published in the field of behavioral science. In general, each measure has a minimum assessment level of 'adequate', with the majority assessed at a level of 'good' or higher.

Instruments selected are well established neuropsychological questionnaires with extensive clinical and research validation and are structured to ensure the highest levels of clarity and ease of administration. Participants will have no difficulty in reliably completing these instruments in a clinical setting. This instrument battery is currently in use in several WRNMMC-approved research projects conducted by the Investigator in both the inpatient ward and outpatient clinics at WRNMMC. Further, this instrument battery is in use by the INTRuST Clinical Consortium, which is a multi-site research collaboration on PTSD and TBI, which will allow de-identified data from this study to be compared across a nationally-representative dataset. Assessments not directly related to the primary outcome are being made to allow for comparability with these other ongoing trials in this population, and all questionnaires were selected and rigorously reviewed to ensure that content overlap was minimized in the interest of participant welfare. As such, no unnecessary measures are included, and all data collected will be analyzed and results reported and disseminated.

**1. Clinician-Administered PTSD Scale (CAPS):** The CAPS (Blake et al 1995; Blake et al., 1990) is a lengthy structured interview based on the DSM-IV that assesses the presence and severity of PTSD and associated symptoms. Changes from baseline to endpoint in the CAPS total score will serve as the primary efficacy measure for the double blind phase. The CAPS is widely accepted as the Gold Standard for establishing PTSD diagnosis with excellent reliability and validity (Blake et al., 1990; 1995), (Weathers et al., 1999).

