**2. Clinical Global Impression of Severity (CGI-Severity):** The CGI-Severity scale (Guy, 1976) will be administered to assess the clinician's global impression of the severity of the patient's PTSD at each visit over the course of treatment. It is a 7-point scale in which 1 = normal and 7 = extremely severe case of PTSD. The CGI is a core metric for psychiatric research and has demonstrated adequate psychometric properties (Berk et al., 2008).

**3. Clinical Global Impression of Improvement (CGI-Improvement):** The CGI-Improvement scale (Guy, 1976) will be administered to assess the clinician's global impression of the improvement of the patient's PTSD over the course of treatment. It is a 7-point scale in which 1 = very much improved, 4 = no change, and 7 = very much worse. A pre-entry score (e.g., for those subjects entering this protocol from other research studies) will be obtained during the screening phase. Those subjects who, at the completion of the previous research study receive scores of 1, 2, or 3 will be excluded from this study.

For this study, treatment response will be defined as those who are very much improved (score of 1), or much improved (score of 2), or improved (score of 3) on the Clinical Global Impressions, improvement item and have a  $\geq 9$  point decrease in CAPS score.

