### 5.7.1 Data Analysis Table

Independent Variable / Predictor	Dependent Variable/ Outcome	Statistical Test
Riluzole/placebo	PTSD anxiety symptomatology (CAPS total score)	t-test/Mann-Whitney U test
Riluzole/placebo	Clinical Response Rate	Pearson's chi-square test, Fisher's exact test
Riluzole/placebo	Effects of treatment status longitudinally	Regression Analysis
Riluzole/placebo	Origin, gender, age, dose level, illness characteristics	ANOVA, Mantel-Haenszel common odds ratio test, Breslow-Day test
Riluzole/placebo	NAA/Cr ratio	t-test/Mann-Whitney U test
Not Applicable	Not Applicable	Descriptive Statistics

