### 11.3 Data Analysis Plan:

**Primary Analysis:** *(Hypothesis 1) Subjects with PTSD randomized to acute therapy with Riluzole will have a superior response rate acutely compared to subjects randomized to placebo.*

The PI will be primarily responsible for data analysis in this study. He will be assisted by a data analyst or analysts within the Department of Psychiatry at USUHS and this person (or persons) will be added to the protocol as investigators (with IRB approval) prior to any handling of the data. The primary intent of this study is to compare the efficacy of riluzole relative to placebo in the treatment of overall anxiety symptomatology of subjects who have PTSD. This will be analyzed by comparing reductions from baseline scores on the CAPS total score after up to 8-weeks of double-blind therapy to the original score before the start of therapy using t-tests or Mann-Whitney U tests when assumptions for t-tests are not satisfied.

In addition to utilizing the CAPS continuous score, scores will also be dichotomized to examine clinical responders versus non-responders in the treatment and placebo groups. A responder will be defined as any patient who demonstrates a 30% or greater decrease in CAPS total score from baseline (phase I) to the last measured value of Phase II. Response rate analyses will then be performed by comparing the proportion of subjects in each treatment group who met the response criteria. Response rates will be analyzed using Pearson's chi-square test or Fisher's exact test when expected cell sizes are less than 5.

In order to more thoroughly assess the effects of treatment status in a longitudinal setting, random effects regression will also be used to examine the study groups over time in the presence of additional covariates.

In general, variables that are continuous, yet non-normally distributed, will be appropriately transformed or will be analyzed using appropriate non-parametric tests. Variables that are non-continuous (ordinal, nominal) will be analyzed using appropriate non-parametric tests. All tests of hypotheses will be tested at a two-sided a level of 0.05.

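### CGI-Severity and CGI-Improvement share the primary-outcome label with CAPS, although other sections make CAPS change the primary variable; the labels, and CGI-Improvement's role in response, should be reconciled

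*Combined protocol and SAP*

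**What the plan says.** Section 9.4 puts three scales under its primary-outcomes item: "Clinician-Administered PTSD Scale (CAPS), Clinical Global Impression of Severity (CGI-Severity), Clinical Global Impression of Improvement (CGI-Improvement". Section 10.2 numbers the same three under the same label before its secondary list begins.

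The same two sections also single out CAPS. Section 9.4 states that "the change in CAPS total score will be the primary outcome variable at the end of Phase II (Visit 10" (the schedule of events numbers its last visit 9). Section 10.2 states: "Changes from baseline to endpoint in the CAPS total score will serve as the primary efficacy measure for the double blind phase".

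The statistical sections are built on CAPS. The power calculation in 11.2 is for a 9-point CAPS difference. The primary analysis in 11.3 compares CAPS reductions, then a CAPS-based responder rate. Yet the hypothesis printed above that analysis is about response: riluzole patients "will have a superior response rate acutely compared to subjects randomized to placebo". On error control, 11.3 says only: "All tests of hypotheses will be tested at a two-sided a level of 0.05".

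No row of table 5.7.1 names either CGI scale. One row is "Clinical Response Rate", and response is defined twice:

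- Section 10.2: "treatment response will be defined as those who are very much improved (score of 1), or much improved (score of 2"; a CGI-Improvement rating of 3 also qualifies, and CAPS must have fallen by at least 9 points as well.
- Section 11.3: "A responder will be defined as any patient who demonstrates a 30% or greater decrease in CAPS total score from baseline", with no CGI component.

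**The concern.** A reader cannot tell from the labels whether the trial has one primary outcome or three. If three, nothing says whether all must succeed, any one is enough, or CAPS comes first. If CAPS missed and a CGI scale reached p<0.05, the primary label on CGI would be available to whoever writes the report, and the CAPS statements would be available to whoever objects. That argument should be closed before unblinding.

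The CGI scales also fall between two parts of the analysis plan. The primary analysis does not name them. The sentence in 11.3 that carries its methods over to other outcomes refers to secondary ones, and CGI is not labelled secondary. What reaches them is the general rule that ordinal variables get a suitable non-parametric test, which fixes no visit and no contrast. CGI-Severity has no other analysis. CGI-Improvement enters only through one of two competing response definitions.

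**Working it through.** **1. The plan's own power figure.** Inputs from 11.2: difference 9, SD 15, 50 per arm, alpha 0.05, two-sample t-test.

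- Degrees of freedom: 2 × 50 − 2 = 98.
- Noncentrality: 9 / (15 × √(2/50)) = 9 / (15 × 0.2) = 3.0.
- Exact noncentral-t power: 0.8439 two-sided and 0.9090 one-sided. The plan states 0.844 and 0.909, so both reproduce.

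This is the power of one CAPS comparison that has the whole 0.05 to itself.

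**2. If any one of the three listed scales counted as success.** This rule is hypothetical; no section states it. With independent tests, the chance of at least one false positive is 1 − 0.95³ = 0.143. The chance of a CGI-only win (a CGI scale significant, CAPS not) is 0.95 × (1 − 0.95²) = 0.95 × 0.0975 = 0.093. For correlated tests, one million draws of three equally correlated normal statistics gave the values below. The documents give no correlations, so these are assumed.

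| Assumed correlation | At least one false positive | CGI-only win |
|---|---|---|
| 0 | 0.143 | 0.093 |
| 0.3 | 0.136 | 0.086 |
| 0.5 | 0.125 | 0.076 |
| 0.7 | 0.109 | 0.059 |
| 0.9 | 0.084 | 0.034 |

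All figures are for a single time point.

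**3. Cost of resolving the conflict each way.**

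- CAPS as sole primary: alpha stays 0.05 and power stays 0.844 with 50 per arm.
- Three alternative primaries with a Bonferroni split: alpha per test is 0.05/3 = 0.0167, exact CAPS power falls to 0.713, and about 65 per arm (normal approximation) would be needed to get back to 0.844.

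**4. The two response definitions.** Entry requires a CAPS score of at least 40, and 30% of 40 is 12 points. For every eligible patient the 11.3 rule therefore demands a larger CAPS fall than the 9 points in 10.2. At a baseline of 80 (an example) it demands 24. A patient who falls 10 points from 40 with CGI-Improvement of 3 is a responder under 10.2 and not under 11.3. A patient who falls 30% but is rated 4 on CGI-Improvement is a responder under 11.3 and not under 10.2.

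**The case against.** The strongest reply is that the plan does name one primary variable. Sections 9.4 and 10.2 both say it is CAPS change, 11.2 powers nothing else, and 11.3 starts from it. On that reading the list in 9.4 is only a grouping of instruments, and CGI-Improvement sits there because it feeds the response rate. Much of this stands, and it rules out several stronger readings that a reader might infer:

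- *The plan permits a primary success on CGI alone.* It does not say so, and such a claim would contradict the CAPS statements. The fault is conflicting labels with no rule to resolve them.
- *CGI is absent from the analysis.* CGI-Improvement can enter through the response-rate row of table 5.7.1 under the 10.2 definition. That definition also requires a CAPS fall of at least 9 points, so CGI alone cannot make a responder. The general rule for ordinal variables covers both scales.
- *The plan subtracts a baseline from CGI-Improvement, which already rates change.* Section 11.3 specifies baseline comparison for CAPS; nothing directs it for CGI-Improvement, and 10.2 uses the raw score. The risk arises only if the scale is moved to secondary without a stated contrast, because 11.3 extends the same techniques to secondary outcomes.
- *The missing CGI power calculation is an error.* It is not if CAPS is the sole primary. It is evidence that CAPS was the intended one.
- *Weekly CGI ratings invite picking a visit.* The schedule shows eight post-baseline CGI ratings (Visits 2 to 9) against two for CAPS (Visits 6 and 9). But 9.4 places the primary outcome at the end of Phase II, 10.2 uses week 8 ratings for response, and 10.2 promises to report all data. The room for selection is limited.

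The reply leaves three things unanswered: the primary label on CGI appears in two sections, no order of testing is given, and response is defined in two incompatible ways under a primary-analysis heading that is itself about response.

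**Conclusion.** The concern holds as a conflict of labels that the plan should resolve. CGI-Severity and CGI-Improvement are called primary in 9.4 and 10.2, against the CAPS-only statements in those sections and the CAPS-only power and primary analysis in 11.2 and 11.3. With every test at 0.05 and no hierarchy, the text does not clearly preclude a primary claim on CGI.

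The 11% to 14% false-positive range rests on two assumptions: a rule that any one of three suffices, which the plan never states, and correlations from 0 to 0.7, which it does not give. It measures what the ambiguity could cost, and is not the error rate of the plan. With CAPS as the only primary outcome, the inflation from these three scales disappears.

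**What to change.** - **9.4 and 10.2:** keep only change in CAPS total score as primary and list both CGI scales as secondary. Align the final visit number in 9.4 with the schedule.
- **11.3 and table 5.7.1, CGI-Improvement:** compare the arms at Visit 9 on the score as given, rated against the patient's state at Visit 1, with no baseline subtraction.
- **11.3 and table 5.7.1, CGI-Severity:** compare the arms at Visit 9 with an ordinal or non-parametric test that takes account of the Visit 1 value.
- **Response:** choose one definition, state it once, and say whether CGI-Improvement is part of it. Rank response rate below CAPS change, and reword Hypothesis 1 and the heading of the primary analysis to match.

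The cost is wording in four places. No visits, ratings or patients are added, and CAPS power stays at 0.844. The sponsor gives up any option of a primary claim on CGI.
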